5.3. Methods to Manage Missing Data

CCI [REDACTED]

In all pharmacokinetic data presentations (except listings), concentrations below the limit of quantification (BLQ) will be set to zero. (In listings BLQ values will be reported as “<LLQ”, where LLQ will be replaced with the value for the lower limit of quantification.)

In summary tables and plots of the median values at each time point, statistics will be calculated having set concentrations to missing if 1 of the following cases is true:

1. A concentration has been collected as ND (ie, not done) or NS (ie, no sample),
2. A deviation in sampling time is of sufficient concern or a concentration has been flagged anomalous by the pharmacokineticist.

Note that summary statistics will not be presented at a particular time point if more than 50% of the data are missing.

6. ANALYSES AND SUMMARIES

6.1. Primary Endpoint: Whole Liver PDFF

6.1.1. Primary Analysis

- **Analysis endpoint:** Whole liver PDFF.
- **Analysis time points:** Day 15.
- **Analysis population:** Full Analysis set
- **Analysis methodology:** Natural log-transformed individual relative change (RC) from baseline to Day 15 in whole liver PDFF will be analyzed using the ANCOVA. Log-transformed baseline will be the covariate. The model will include natural log-transformed baseline whole liver PDFF and diabetes status. If there is substantial imbalance in the number of subjects enrolled in each site then study site and interaction of study site with treatment will be considered to be included as potential covariates.

Reporting results:

- **Raw data:** The sample size, mean, standard deviation, median, minimum and maximum at baseline and Day 15 visit will be presented for each treatment arm.
- **%CBL:** The sample size, mean, standard deviation, median, minimum and maximum will be presented for each treatment arm at Day 15. The LSMs and their 80% CI will be exponentiated to provide estimates of the RC which will be converted to percent change as follows:

$$\text{Percent change} = 100 * (\text{RC} - 1).$$

The LSMs of the percent change from baseline with the 80% CIs for each treatment group and the LSMs of the percent change from placebo with the 80% CIs for each of the PF-06865571 groups and the 2-sided p-values will be presented.

Figures

- Whole liver PDFF - Bar chart of the model-derived least square means for all treatment groups including the placebo group with 80%CI will be provided for Day 15 with treatment group on the X-axis.
- Whole liver PDFF - Bar chart of the placebo-adjusted least square means with 80%CI for the two PF-06865571 treatment groups will be provided for Day 15 with dose on the X-axis.

- Whole liver PDFF - Box and whisker plots for individual percent change from baseline versus treatment will be presented and overlaid with arithmetic means.

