3.4. Baseline Variables

Baseline variables are those collected on Day 1 prior to dosing or before Day 1. The demographic data of age, race, weight, and body mass index will be summarized by sex at birth and treatment in accordance with the sponsor reporting standards. Ethnicity will not be summarized. The number and proportion of subjects enrolled in each study site will also be presented.

In this study subjects will be stratified at randomization based on the presence or absence of Type 2 Diabetes Mellitus (T2DM) and by the MRI-PDFP liver fat categories obtained during Visit 3 (Screen 3) listed below:

- Screening liver fat $\geq 6\%$ and $< 10\%$;
- Screening liver fat $\geq 10\%$.

Both of these stratification variables will be used as covariates in the efficacy analysis. For baseline diabetic status, data will be obtained from the case report forms (CRFs). Even though baseline liver fat was used as a binary variable for stratification purposes, it will be used as a continuous covariate in the efficacy analysis in order to maximize the utility of information. If there is substantial imbalance in the number of subjects enrolled in each site then study site will be considered to be included as a potential covariate. If included as a covariate sites enrolling less than 6 subjects will be pooled.

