5.2. General Methods

Descriptive Statistics

Descriptive statistics, including the sample size, mean, standard deviation, median, minimum, and maximum values, will be provided for continuous endpoints. Some measures will be summarized using graphical representations by treatment and study day of visit, where appropriate.

Analysis of Covariance (ANCOVA)

The ANCOVA model will be used with continuous endpoints for landmark (single time point) analyses. The model will include treatment group as fixed effect, baseline value of the endpoint being analyzed, baseline whole liver PDFF and baseline diabetes status as covariates. If there is substantial imbalance in the number of subjects enrolled in each site then study site and interaction of study site with treatment will be considered to be included as potential covariates for the analysis of primary endpoint only. If included as a covariate, sites enrolling less than 6 subjects will be pooled. The number of covariates may be reduced to improve model fit. Estimates of treatment effects will be assessed using LSMs and CIs. Estimates of the mean differences between each active dose and placebo, and the corresponding 80% CI will be obtained from the model. Comparison of each PF-06865571 dose with the placebo will be performed at a Type I error rate of 10% (1-sided). If there are major deviations from the statistical assumptions underlying this model then alternative transformations (eg, log) or non-parametric analyses may be presented. Justification for any alternative to the planned analysis will be given in the study report.

Non-parametric Analysis

If the data have many outliers even after the log-transformation the following non-parametric analysis will be performed instead of the linear model. An outlier will be defined as any datapoint falling outside of $3.5 \times$ standard deviations \pm the median. Additional evaluative statistics will be conducted to explore the nature of the outliers in order to determine the appropriateness of a parametric analysis.

For group medians 80% CIs will be presented. In addition the 80% CIs will also be presented for differences in group medians from placebo group median. The method of McGill, Tukey, and Larson¹ will be employed to calculate the CI for the difference in treatment group medians.

CCI [REDACTED]

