6.1.2. Sensitivity/Robustness Analyses

- **Analysis endpoint:** Whole liver PDFF.
- **Analysis time points:** Day 15.
- **Analysis population:** Full Analysis set.
- **Analysis methodology:** %CBL to Day 15 in whole liver PDFF will be analyzed using the ANCOVA. The model will include baseline whole liver PDFF and diabetes status. If there is substantial imbalance in the number of subjects enrolled in each site then study site and interaction of study site with treatment will be considered to be included as potential covariates.

Reporting results:

The LSMs, 80% CI for the LSMs, difference between the LSM of each treatment group and the placebo group, and the corresponding 80% CI and the 2-sided p-values will be presented for whole liver PDFF.

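### SAP 5.2 and 6.1.1 allow an optional site-by-treatment term in the primary liver-fat ANCOVA; if used with about 42 completers, the dose-placebo contrast loses precision and may not be estimable

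*SAP*

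**What the plan says.** Protocol 9.2.1 defines the primary model: ANCOVA on log relative change in whole liver PDFF, with treatment and baseline diabetic status as factors and log baseline PDFF as covariate. It has no site term. The default model in SAP 6.1.1 agrees.

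The SAP then adds an option, triggered by an imbalance in site enrolment for which it gives no threshold:

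- SAP 6.1.1 (primary analysis): "then study site and interaction of study site with treatment will be considered to be included as potential covariates".
- SAP 5.2 repeats it, with both terms "considered to be included as potential covariates for the analysis of primary endpoint only".
- SAP 6.1.2 (sensitivity analysis on percent change) has the same option.
- SAP 3.4 uses the same trigger but names site alone: "study site will be considered to be included as a potential covariate".

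Three rules in SAP 5.2 bear on its use: "sites enrolling less than 6 subjects will be pooled"; "The number of covariates may be reduced to improve model fit"; and "Justification for any alternative to the planned analysis will be given in the study report". Protocol 9 and SAP 2 also send major modifications of the primary analysis to a protocol amendment.

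About 4 to 6 sites are planned (SAP 2.2). Randomization uses permuted blocks, stratified by screening liver fat and T2DM (protocol 4.3). Site is not a listed stratum.

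**The concern.** Once treatment interacts with site, the dose-placebo effect is an average of site-specific effects. Its value and its standard error then depend on the site weights, and the readable text gives none.

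Pooling stops at 6 subjects, so a unit of 6 is allowed, which averages two subjects per arm. Since site is not a listed stratum, such a unit can lack an arm altogether. That arm's least-squares mean is then not estimable under any weighting that includes the site. If the missing arm is placebo, both dose contrasts are lost. No empty-cell rule appears in the readable text.

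At stake is the precision, and in some layouts the existence, of the main estimate in a trial with 14 completers per arm.

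**Working it through.** **Inputs from protocol 9.1.** 25% reduction, so effect |ln 0.75| = 0.2877; SD 0.36; 1-sided alpha 0.10; 42 completers, taken as 14 per arm.

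**The plan's own figure.** SE = 0.36 × √(2/14) = 0.1361. Normal power = Φ(0.2877/0.1361 − 1.2816) = Φ(0.833) = 79.8%. Noncentral t gives 79.1% with 39 df, and also with the 37 df of the protocol ANCOVA. The stated 79% reproduces.

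**Interaction model.** With S site units and weights w_s, ignoring covariate imbalance:

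SE² = 0.36² × Σ w_s² (1/n_s,active + 1/n_s,placebo), df = 42 − 3S − 2.

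*By hand, assumed layout 24/6/6/6 with arms equal within site.* Each arm has n_s/3 subjects, so the bracket is 6/n_s.

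- Equal weights (1/4 each): (6/24 + 3 × 6/6)/16 = 3.25/16 = 0.2031, against 2/14 = 0.1429 without site. SE ratio = √(0.2031/0.1429) = 1.19; power 67.9% on 28 df.
- Size weights (n_s/42): Σ (n_s/42)² × 6/n_s = 6/42 = 0.1429. There is no SE loss, only fewer df.

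So both the weights and the within-site balance matter.

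*Empty cells, by hand.* With 14/14/14 allocated at random, a given unit of 6 lacks a given arm with probability C(28,6)/C(42,6) = 376,740/5,245,786 = 0.072. It lacks at least one of the two arms in a given contrast with probability 2 × 0.072 − C(14,6)/C(42,6) ≈ 0.143. Treating units as independent, three such units give 1 − 0.857³ ≈ 37% and five give 1 − 0.857⁵ ≈ 54%. Simulation gave 38% and 54%.

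**Main illustration.** Assumed: 3 to 6 units; permuted blocks of 3 within the liver-fat and T2DM strata, ignoring site; strata of 10, 22, 3 and 7 subjects (10 of 42 diabetic); residual SD held at 0.36. Power comes from the full design matrix, averaged over simulated allocations; for the interaction model, only allocations with every cell filled are used.

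| Model | Power |
|---|---|
| Protocol 9.2.1 | about 79% |
| Interaction, equal site weights | about 61-71% |
| Interaction, site-size weights | about 72-75% |

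The chance of an empty cell in a given dose-placebo contrast runs from about 2% (20/12/10) to 58% (12/6/6/6/6/6).

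**By layout, with allocation fully random instead.** The protocol model then gives 77.5%, because diabetic status and baseline are also left to chance.

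| Layout | Power, equal / size weights | Empty cell, given contrast | Any empty cell |
|---|---|---|---|
| 20/12/10 | 70% / 73% | 2% | 4% |
| 16/10/8/8 | 69% / 72% | 12% | 17% |
| 18/12/6/6 | 65% / 73% | 28% | 39% |
| 24/6/6/6 | 60% / 74% | 38% | 51% |
| 12/6/6/6/6/6 | 68% / 71% | 54% | 69% |

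Across the 3-6 unit layouts examined under random allocation, the 80% CI is 13-32% wider (equal weights) or 6-13% wider (size weights) than under the protocol model.

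**Favourable case.** With arms in blocks of 3 within site, no cells are empty. Power is 66-74% with equal weights and 76-77% with size weights, so the size-weighted loss is about 1-2 points.

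**Break-even under random allocation.** To regain the protocol model's power, the site terms must explain 10-21% of residual variance (interaction, size weights), 22-42% (interaction, equal weights) or 5-14% (additive site). The documents give no between-site variance.

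**The case against.** The strongest reply is that nothing here is mandatory. The trigger is conditional and inclusion is only to be considered. The default model matches the protocol, small sites are pooled, and an interaction that cannot be estimated could be dropped under the covariate-reduction clause. Departures must be justified in the report, and a major one needs an amendment. All of this stands and keeps the severity low. It does not settle the matter: none of these clauses says whether the interaction would stay in the primary model, and the documents do not say whether adding it counts as major.

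It is also fair that the large losses need equal site weights, that every layout is assumed, and that site terms might explain enough variance to pay for themselves. The figures are illustrations, not predictions.

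A reader might go further in four ways that the documents do not support:

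- *That the type I error is inflated.* A trigger based on enrolment counts alone does not do this.
- *That the protocol model misses its stated power.* The 77.5% comes from ignoring the stratification; the stated figure reproduces.
- *That the SAP has no weighting or empty-cell rule at all.* SAP 5.2 ends, and 5.3 begins, with redacted text, so this can be said only of the readable text.
- *That an additive site term is also a mistake.* Under random allocation it gives 72.9-75.7% against 77.5%, and it pays for itself once site explains 5-14% of residual variance. That is a judgement call.

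**Conclusion.** The point holds as a cheap improvement of low severity. SAP 5.2 and 6.1.1 permit a term in the primary model that protocol 9.2.1 does not contain and SAP 3.4 does not name. If it is used with 42 completers, power falls from about 79% to roughly 61-71% or 72-75%, depending on the weights, and a given contrast may not be estimable. This rests on assumed layouts of 3-6 units, 10 of 42 diabetic, residual SD 0.36 and allocation that ignores site. With arms balanced within site and size weights, little is lost. The same option in SAP 6.1.2 affects a sensitivity analysis and not the primary contrast. It does not follow that the trial will be underpowered, because the option may never be used.

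**What to change.** Delete the site-by-treatment interaction from the primary-endpoint model in SAP 5.2 and 6.1.1. The dose-placebo contrast then always comes from a model without it, and the text agrees with SAP 3.4. Show PDFF results by site beside the counts already planned ("The number and proportion of subjects enrolled in each study site will also be presented"), or fit the interaction only as a labelled exploratory analysis when every site-by-arm cell is filled. Allocation counts show whether cells are filled, without Day 15 PDFF data.

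Whether additive pooled site remains an option in the primary model is for the sponsor. If the protocol 9.2.1 model is to be the only primary model, the study-site wording in SAP 3.4, 5.2 and 6.1.1 must go too; removing the interaction alone would not achieve that.

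The cost is SAP wording. The downside is that site heterogeneity is described, not modelled, in the primary analysis.

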6.1.2. Sensitivity/Robustness Analyses

- **Analysis endpoint:** Whole liver PDFF.
- **Analysis time points:** Day 15.
- **Analysis population:** Full Analysis set.
- **Analysis methodology:** %CBL to Day 15 in whole liver PDFF will be analyzed using the ANCOVA. The model will include baseline whole liver PDFF and diabetes status. If there is substantial imbalance in the number of subjects enrolled in each site then study site and interaction of study site with treatment will be considered to be included as potential covariates.

Reporting results:

The LSMs, 80% CI for the LSMs, difference between the LSM of each treatment group and the placebo group, and the corresponding 80% CI and the 2-sided p-values will be presented for whole liver PDFF.

6.2. Secondary Endpoint(s)

The analyses of safety endpoints will be described in [Section 6.6](#).

Presentations for PF-06865571 concentrations will include:

- A listing of all concentrations sorted by dose, subject ID, day and nominal time post dose. The listing of concentrations will include the actual sample collection times, and the time of dosing. Deviations from the nominal time will be given in a separate listing.
- A summary of concentrations by dose, day, and nominal time post dose, where the set of statistics will include n, mean, median, standard deviation, coefficient of variation (CV), minimum, maximum and the number of concentrations above the LLQ.
- A median plot of steady state (Day 14) plasma concentrations by dose will be provided.
- The PK parameters listed in [Section 3.2](#) will be summarized descriptively by dose.

CCI

CCI

CCI

CCI

6.4. Subset Analyses

For the primary endpoint subset analysis by the whole liver PDFF stratification categories provided below may be considered.

- Screening liver fat $\geq 6\%$ and $< 10\%$;
- Screening liver fat $\geq 10\%$.

CCI

6.5. Baseline and Other Summaries and Analyses

A breakdown of demographic data will be provided for age, race, weight, and body mass index. Each will be summarized by sex at birth and treatment in accordance with the sponsor reporting standards. Baseline summary of parameters of interest, namely, fasting glucose, CCI waist circumference, AST, ALT, alkaline phosphatase, GGT and whole liver PDFF will be presented for each treatment group and overall. Baseline summary

of stratification factors, namely, diabetes status (presence or absence) and MRI-PDFF categories ($\geq 6\%$ and $< 10\%$ or $\geq 10\%$) will be provided. The number and proportion of subjects enrolled in each study site will also be presented.

Subject evaluation groups will show end of study subject disposition and will show which subjects were analyzed for pharmacodynamic (FAS) and pharmacokinetics (PK), as well as for safety (AEs and laboratory data). Frequency counts will be supplied for subject discontinuation(s) by treatment. Data will be reported in accordance with the sponsor reporting standards.

6.6. Safety Summaries and Analyses

A set of summary tables split by treatment will be produced to evaluate any potential risk associated with the safety and toleration of administering PF-06865571.

The standard safety endpoints detailed in Section 3.5 will be listed and summarized in accordance with sponsor reporting standards, where the resulting data presentations will consist of subjects from the safety analysis sets. The analyses of non-standard safety data will also utilize safety analysis set and the methods are described below.

Any untoward findings identified on physical examinations conducted during the active collection period will be captured as AEs, if those findings meet the definition of an AE. Data collected at screening that are used for inclusion/exclusion criteria, such as laboratory data, ECGs, and vital signs, will be considered source data, and will not be required to be reported, unless otherwise noted.

6.6.1. Adverse Events

Adverse events will be summarized by treatment and in accordance with current Pfizer data standards. The AEs will be sorted alphabetically within a system organ class. Summary tables will be provided for TEAEs and AEs occurring prior to randomization will only be listed.

The 3-Tier approach will not be used to summarize the AEs due to the small sample size.

6.6.2. Laboratory Data

All planned, quantitative, standard safety laboratory data presented in Table 6 of the protocol and non-standard safety laboratory data that are not reported independently will be listed and summarized at each collection time point by treatment in accordance with the sponsor reporting standards as applicable. Baseline is as defined in [Section 3.5.2](#).

6.6.3. Vital Signs

Absolute values and changes from baseline in supine systolic and diastolic blood pressure and pulse rate will be summarized by treatment and study day, according to sponsor reporting standards. Tables will be paged by parameter. Baseline is as defined in [Section 3.5.3](#).

Mean changes from baseline for systolic and diastolic blood pressure and pulse rate will be plotted against study day. On each plot there will be 1 line for each treatment, all treatments on the same plot including the placebo.

For baseline subtracted supine systolic and diastolic blood pressure and pulse rate, the differences between each dose and placebo (dose – placebo) will be summarized (N, mean, 90% CI) and plotted (mean, 90% CI) for each dose and day.

Maximum absolute values and maximum changes from baseline for vital signs, over all measurements taken post dose will also be tabulated by treatment using categories as defined in the Appendix. Numbers and percentages of subjects meeting the categorical criteria will be provided. All planned and unplanned post dose time points will be counted in these categorical summaries. All values meeting the criteria of potential clinical concern will be listed.

Maximum decrease and increase from baseline for supine systolic and diastolic blood pressures, and maximum increase from baseline for supine pulse rate will be summarized by treatment, according to sponsor reporting standards.

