6.6.4. Electrocardiogram

Average of the triplicate measurements will be used in all analyses. Absolute values and changes from baseline in QT, heart rate, QTcF, PR, RR and QRS will be summarized by treatment and day using sponsor reporting standards. Tables will be paged by parameter. Baseline is as defined in Section 3.5.4.

Mean changes from baseline in QT, heart rate and QTcF will be plotted against study day. On each plot there will be 1 line for each treatment, all treatments on the same plot including the placebo.

In addition for baseline subtracted QT, heart rate and QTcF, the differences between each dose and placebo (dose – placebo) will be summarized (N, mean, 90% CI) and plotted (mean) for each dose and day including follow-up.

ECG endpoints and changes from baseline (QTcF, PR and QRS) will also be summarized descriptively by treatment using categories as defined in the Appendix (for QTc these correspond to ICH E14). Numbers and percentages of subjects meeting the categorical criteria will be provided. All planned and unplanned postdose timepoints will be counted in these categorical summaries. All values meeting the criteria of potential clinical concern will be listed.

Maximum absolute value (post dose) and the maximum increase from baseline for QTcF, PR and QRS will be summarized by treatment according to sponsor reporting standards.

Listings of subjects with any single post dose value > 500 msec will also be produced for QTcF.

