6.6.5. Non-standard Safety Analysis

Serum Creatinine, Serum Cystatin C and Associated eGFRs

Absolute values and changes from baseline in serum creatinine, serum cystatin C, eGFRs obtained from serum creatinine and cystatin C will be summarized by treatment and day. Mean absolute values of all four parameters will be plotted separately against study day. On each plot there will be 1 line for each treatment, all treatments on the same plot including the placebo. Mean changes from baseline in eGFRs will also be plotted against study day.

Liver Function Tests

Raw values, change and %CBL in ALT, AST, Total Bilirubin, GGT, and alkaline phosphatase will be summarized by treatment at all relevant collection time points including follow-up. For %CBL group medians and differences in group medians from placebo with 80% CIs will be presented. Line plot of medians with 80% CIs for all treatment groups including the placebo group with study day on X-axis will be provided. Three lines corresponding to the 3 treatment groups will be overlaid on the same plot.

Body Weight

Raw values, change and %CBL in body weight will be summarized by treatment at all relevant collection time points including follow-up. For %CBL group medians and differences in group medians from placebo with 80% CIs will be presented. Line plot of medians with 80% CIs for all treatment groups including the placebo group with study day on X-axis will be provided. Three lines corresponding to the 3 treatment groups will be overlaid on the same plot.

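### The placebo comparisons for vital signs and ECG are worded as change scores without a baseline covariate; adding each parameter's own baseline would be a small, nearly free gain in precision

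*SAP*

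**What the plan says.** **Vital signs (SAP 6.6.3).** "For baseline subtracted supine systolic and diastolic blood pressure and pulse rate, the differences between each dose and placebo" are the quantities compared, and they "will be summarized (N, mean, 90% CI) and plotted (mean, 90% CI) for each dose and day".

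**ECG (SAP 6.6.4).** "In addition for baseline subtracted QT, heart rate and QTcF, the differences between each dose and placebo" are summarized with N, mean and 90% CI by dose and day, follow-up included. The input is a triplicate mean: "Average of the triplicate measurements will be used in all analyses".

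**Baseline (SAP 3.5.3 and 3.5.4).** It is the result closest before dosing on Day 1. Protocol Table 2 schedules a single supine vital-sign reading and a triplicate ECG.

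**General model (SAP 5.2).** "The ANCOVA model will be used with continuous endpoints for landmark (single time point) analyses". On its terms, "The model will include treatment group as fixed effect, baseline value of the endpoint being analyzed", and baseline liver PDFF and diabetes status are also included. Its interval level differs from that of the safety sections: "Estimates of the mean differences between each active dose and placebo, and the corresponding 80% CI will be obtained from the model".

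**Other safety intervals (SAP 6.6.5).** Liver tests and body weight follow another method: "For %CBL group medians and differences in group medians from placebo with 80% CIs will be presented".

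**Status of the safety analysis (Protocol 9.6).** Safety data are to be summarized descriptively where appropriate.

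**The concern.** Subtracting baseline fixes the regression slope of the post-dose value on baseline at 1. If the true slope is lower, an arm that starts high by chance tends to fall back and an arm that starts low tends to rise. The change score then carries part of the starting difference into the dose-minus-placebo estimate.

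Four features of this trial make that relevant:
- The arms are small, about 15 each.
- Randomization is stratified on liver fat and T2DM only (Protocol 4.3), so nothing balances baseline blood pressure, pulse or QTcF.
- The same Day 1 baseline is subtracted on every study day, so an imbalance recurs at each time point and can look like a sustained effect.
- Both dose contrasts share the placebo baseline, so an unusual placebo arm moves both in the same direction.

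Within SAP 6.6.3 and 6.6.4 these differences are the only between-arm estimates with intervals, and safety is a secondary objective. There is also an ambiguity: a programmer who applied SAP 5.2 would produce different estimates from one who took 6.6.3 and 6.6.4 at face value.

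**Working it through.** **Inputs from the documents.** Three arms, 1:1:1, about 15 per arm, at least 42 completers, hence 42/3 = 14 per arm (Protocol 3.1 and 9.1); 90% CIs (SAP 6.6.3, 6.6.4). The documents state no precision for the safety differences, so there is no figure of that kind to reproduce. The sample-size figure does reproduce: at 14 per arm, effect ln(0.75) = -0.2877, SD 0.36 and 1-sided alpha 0.10, the normal approximation gives 79.75%, against the stated minimum of 79%.

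**Assumptions.** Equal SD s at baseline and post-dose, and correlation r between them, taken over a range. The documents give neither.

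**Step 1: large-sample variance per subject.**
- Change score: 2s²(1-r).
- ANCOVA with own baseline: s²(1-r²).
- SE ratio, ANCOVA to change score: sqrt((1+r)/2).

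**Step 2: finite-sample 90% half-width, three arms pooled, n per arm.**
- Change score: t(0.95; 3n-3) × s × sqrt(2(1-r)) × sqrt(2/n).
- ANCOVA: t(0.95; 3n-4) × s × sqrt(1-r²) × sqrt(2/n) × sqrt(1 + 1/(3n-5)). The last factor is the cost of estimating the slope.

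At n = 14, t is 1.6849 (39 df) for the change score and 1.6860 (38 df) for ANCOVA, and the slope factor is sqrt(1 + 1/37) = 1.0134.

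| r (assumed) | Change score, units of s | ANCOVA, units of s | ANCOVA narrower by |
|---|---|---|---|
| 0.5 | 0.637 | 0.559 | 12.2% |
| 0.6 | 0.570 | 0.517 | 9.3% |
| 0.7 | 0.493 | 0.461 | 6.5% |
| 0.8 | 0.403 | 0.388 | 3.8% |
| 0.9 | 0.285 | 0.282 | 1.2% |
| 0.95 | 0.201 | 0.202 | -0.1% |

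At n = 15 the last column is 12.3%, 9.4%, 6.6%, 3.9%, 1.3% and 0.0%. Simulation with 20,000 trials per value of r agrees with both sets to within 0.1 percentage point. In the same simulation both methods had coverage between 0.89 and 0.91 and average bias of essentially zero.

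**Step 3: conditional shift.** Given a baseline difference D (dose minus placebo), the expected change-score estimate is the true effect minus (1-r)D. The simulated slopes on D at n = 14 were -0.499 at r = 0.5, -0.302 at 0.7 and -0.102 at 0.9, as the formula predicts.

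**Step 4: illustration in mmHg.** Assume a systolic SD of 12 mmHg (not in the documents) and n = 15.
- SE of the baseline difference: 12 × sqrt(2/15) = 4.38 mmHg.
- Shift from an imbalance of one SE: 4.38 × (1-r) = 2.2, 1.8, 1.3 and 0.9 mmHg at r = 0.5, 0.6, 0.7 and 0.8.
- 90% half-width at r = 0.6: 6.6 mmHg for the change score and 6.0 mmHg for ANCOVA.

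**The case against.** **The analysis as worded is valid.** This stands. Under randomization the difference in mean change is unbiased on average, and its interval covers at the stated level. The interval already allows for chance imbalance: in the illustration the 1.8 mmHg shift is about a quarter of the 6.6 mmHg half-width. A reader might infer that the plan builds a bias into its safety estimates. It does not; the shift is conditional on the sample drawn.

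**The loss depends on an unknown correlation.** This also stands. At r of 0.9 and above there is almost nothing to gain. Averaging triplicate ECGs, and taking scheduled inpatient readings before the morning dose, may push r toward that end. A two-arm ANCOVA at 14 per arm would even be 0.9% wider than the two-arm change score at r = 0.95. With all three arms in the model the two are equal at 0.95, and at 0.97 the ANCOVA interval is 0.6% wider, which is immaterial.

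**Not all safety intervals are of this kind.** A reader might take the point to cover every safety interval. SAP 6.6.5 rules that out: liver-test and body-weight intervals are differences in medians of percent change. Creatinine, cystatin C and eGFR have no stated interval.

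**SAP 5.2 might already apply.** Its general rule could be read to cover these endpoints, and 6.6.3 and 6.6.4 do not exclude it. But they do not cite it, they use 90% rather than 80% intervals, and they mention no covariate. The unadjusted reading is the natural one, though the SAP does not state it outright. Either way the method needs to be named.

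**The outputs are descriptive.** This stands and sets the severity. No margin or decision rule is attached to these intervals. The categorical tables, listings and maximum-change summaries would not change under ANCOVA, and the SAP's category for systolic change is 30 mmHg.

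**Conclusion.** The point holds as a minor, nearly free improvement. As worded, the dose-minus-placebo differences in blood pressure, pulse, QT, heart rate and QTcF are change scores without a baseline covariate, although own-baseline adjustment is the SAP's general method for single-time-point analyses.

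The gain is worthwhile at moderate correlation (roughly 4% to 12% of interval width for r from 0.8 down to 0.5), negligible at 0.9, and nil at 0.95. The sensitivity to chance baseline imbalance, (1-r) per unit, follows the same pattern. These sizes rest on assumed correlations and equal variances; the mmHg figures rest also on an assumed SD of 12.

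The documents do not support a claim that the safety estimates are invalid or biased on average. The primary analysis and the sample size are untouched.

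**What to change.** In SAP 6.6.3 and 6.6.4, state that each day's dose-minus-placebo difference and its 90% CI come from an ANCOVA of change from baseline, with treatment (all three arms) as factor and that parameter's own baseline as covariate. Say that this replaces the SAP 5.2 covariate set and 80% level for these outputs. Keep the raw mean-change tables and plots.

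If the sponsor prefers the simple difference in mean change, say so explicitly, so that the method behind the intervals is fixed before unblinding.

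Cost: one sentence in each section and one model call per parameter and day. No new data are needed, because every baseline is already collected.
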